1. OBJECTIVES

1.1 Primary Objectives:

1. To compare rates of all-cause mortality in the 180 days following enrolment for an episode of high risk diarrhoea without dysentery among children 2 to 23 months of age living in low resource settings who are randomized to receive a 3-day course of azithromycin or placebo.
2. To compare the change in linear growth (Δ LAZ) in the 90 days following enrolment for an episode of high risk diarrhoea without dysentery among children 2 to 23 months of age living in low resource settings who are randomized to receive a 3-day course of azithromycin or placebo.

1.2 Secondary Objectives:

1. To compare changes in markers of acute malnutrition (Δ MUAC and Δ WLZ and Δ weight) in the 90 days following an episode of high risk diarrhoea without dysentery among children 2 to 23 months of age living in low resource settings who are randomized to receive a 3-day course of azithromycin or placebo.
2. To evaluate (as determined by verbal and social autopsy- VASA) cause-specific mortality rates across randomization arms in the 180 days following an episode of high risk diarrhoea without dysentery among children 2 to 23 months of age living in low resource settings who are randomized to receive a 3-day course of azithromycin or placebo.
3. To compare the proportion of children hospitalized in the 90 days following enrolment for an episode of high risk diarrhoea without dysentery among children 2 to 23 months of age living in low resource settings who are randomized to receive a 3-day course of azithromycin or placebo.
4. To compare the proportion of children hospitalized or died in the 90 days following enrolment for an episode of high risk diarrhoea without dysentery among children 2 to 23 months of age living in low resource settings who are randomized to receive a 3-day course of azithromycin or placebo.
5. To compare the proportion of children hospitalized or died in the 10 days following enrolment for an episode of high risk diarrhoea without dysentery among children 2 to 23 months of age living in low resource settings who are randomized to receive a 3-day course of azithromycin or placebo.
6. To compare the proportion of strains of *Escherichia coli* (*E. coli*), isolated from stools, resistant to selected antibiotics at enrolment among the study population. Since children entering later into the trial are coming from the same communities, they can serve as a comparator group indicative of the community level of resistance.

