6.4 Outcome measurements

- **Mortality** and date of death to be ascertained at the DAY 45 contact, the DAY 90 and DAY 180 visits, or at any other time point during the 180-day study period. **Verbal and Social Autopsies (VASA)** will be attempted for all recorded deaths within the study period. As part of the VASA autopsy procedures for deaths that occur in facilities, we will collect all available relevant information (diagnostics, treatment and drugs, etc.) from the medical record file of the study subject.
- **Hospitalizations** (number and categorized causes) between days 0 and 180
- **Anthropometric measurements:** length or height, weight and MUAC will be measured at enrolment and at the DAY 90 visit.
- **Antimicrobial resistance** prevalence of phenotypic resistance to selected antibiotics in isolated *E. coli* (stool sample), and *S. pneumoniae* (naso-pharyngeal swabs) at enrolment, at DAY 90 and at DAY 180 will be measured on a sub-sample. Additionally, stool samples will be stored from all children at enrolment, to facilitate later molecular identification of diarrhea etiologies, gut microbiota, and antimicrobial resistance genes in stool bacteria. For the same purpose, stool and nasopharyngeal swab samples will be stored on DAY 90 and DAY 180 from the sub-sample of children (see sections 6.5 and 6.6 for further details).

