10.2 Secondary Objectives

1. *To compare changes in markers of acute malnutrition (Δ MUAC and Δ WLZ and Δ weight) in the 90 days following an episode of high risk diarrhoea without dysentery among children 2 to 23 months of age living in low resource settings who are randomized to receive a 3-day course of azithromycin or placebo.*

Linear regression (and associated z-test) will be used to compare mean Δ MUAC and Δ WLZ and weight across the treatment groups among surviving children.

2. *To evaluate (as determined by Verbal and Social Autopsy – VASA) cause-specific mortality rates across randomization arms in the 180 days following an episode of high risk diarrhoea without dysentery among children 2 to 23 months of age living in low resource settings who are randomized to receive a 3-day course of azithromycin or placebo.*

We will conduct Cox regression and K-M survival analyses (as described for aim 1) for time to cause-specific mortality (diarrhoea, pneumonia, malnutrition, other) as separate endpoints to understand intervention effects on specific causes of death.

3. *To compare the proportion of children hospitalized in the 90 days following enrolment for an episode of high risk diarrhoea without dysentery among children 2 to 23 months of age living in low resource settings who are randomized to receive a 3-day course of azithromycin or placebo.*

4. *To compare the proportion of children hospitalized or dying in the 90 days following enrolment for an episode of high risk diarrhoea without dysentery among children 2 to 23 months of age living in low resource settings who are randomized to receive a 3-day course of azithromycin or placebo.*

5. *To compare the proportion of children hospitalized or dying in the initial 10 days following enrolment for an episode of high risk diarrhoea without dysentery among children 2 to 23 months of age living in low resource settings who are randomized to receive a 3-day course of azithromycin or placebo.*

6. *To compare the presence of strains of *E. coli* resistant to selected antibiotics at enrolment between children in the different treatment arms entering the trial over time. Since children entering later into the trial are coming from the same communities, they can serve as a comparator group indicative of the community level of resistance.*

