1. To compare rates of all-cause mortality in the 180 days following enrolment for an episode of high risk diarrhea without dysentery among children 2 to 23 months of age living in low resource settings who are randomized to receive a 3-day course of azithromycin or placebo.
2. To compare the change in linear growth (Δ LAZ) in the 90 days following an episode of high risk diarrhea without dysentery among children 2 to 23 months of age living in low resource settings who are randomized to receive a 3-day course of azithromycin or placebo.

3.2 Secondary Objectives:

Following an episode of high risk diarrhea without dysentery among children 2 to 23 months of age living in low resource settings who are randomized to receive a 3-day course of azithromycin or placebo, comparison by trial allocation arm of:

1. proportion of children with at least one hospitalization in the 90 days following enrolment
2. proportion of children with at least one hospitalization or who died in the 90 days following enrolment.
3. proportion of children with at least one hospitalization or who died in the initial 10 days following enrolment.
4. change in weight-for-length Z-score (Δ WLZ) in the 90 days following enrolment.
5. change in weight-for-length Z-score (Δ WAZ) in the 90 days following enrolment.
6. change in mid-upper arm circumference (Δ MUAC) in the 90 days following enrolment.
7. Prevalence of azithromycin resistant *E.coli* at baseline among a random subsample of enrolled participants.
8. Prevalence of azithromycin resistant *E.coli* and azithromycin resistant *S. pneumoniae* at D90 and D180 among a random subsample of enrolled participants and their household contacts.
9. Describe cause-specific mortality rates (as determined by verbal autopsy) in the 90 days following enrolment.

3.3 Trial implementation process outcomes:

By trial allocation arm:

1. Describe baseline characteristics
2. Describe dose compliance

3. Proportion of children with a documented serious adverse event in the initial 10 days following enrolment
4. Describe protocol deviations

By country of enrolment:

5. Describe baseline characteristics by country of enrolment
6. Describe dose compliance by country of enrolment

4 General approach to data analysis

4.1 Intention to treat (ITT) analysis:

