$$\mathbf{X}_{ij} = \begin{cases} \text{age category } (< 6m, 6 - 11m, \geq 12m) \\ \quad + \text{Sex} \\ \quad + \text{Wealth quintile} \end{cases}$$

Where randomization resulted in imbalanced covariates, sensitivity analysis will include in vector \mathbf{X}_{ij} confounders that are imbalanced (e.g. but not limited to: sex, wasting, stunting, dehydration) as previously described.

9.4 Analysis of secondary endpoint 4, 5 & 6

Secondary endpoint 4 & 5: To compare Δ WLZ and Δ MUAC in the 90 days following an episode of high risk diarrhea without dysentery among children 2 to 23 months of age living in low resource settings who are randomized to receive a 3-day course of azithromycin or placebo.

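### The protocol's change-in-weight secondary endpoint is not analysed in the SAP; ΔWAZ takes its place and the replacement is not recorded

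*SAP*

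**What the plan says.** **Protocol.** Section 1.2, objective 1: "To compare changes in markers of acute malnutrition (Δ MUAC and Δ WLZ and Δ weight) in the 90 days following an episode". Section 10.2 plans a linear regression with a z-test to "compare mean Δ MUAC and Δ WLZ and weight across the treatment groups among surviving children". Section 6.4 provides the data: "length or height, weight and MUAC will be measured at enrolment and at the DAY 90 visit".

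**SAP.** Section 3.2 gives item 4 as "change in weight-for-length Z-score (Δ WLZ) in the 90 days following enrolment", item 5 as "change in weight-for-length Z-score (Δ WAZ) in the 90 days following enrolment" and item 6 as ΔMUAC. The null and alternative hypotheses for objectives 4 to 6 (section 5) name ΔWLZ, ΔWAZ and ΔMUAC, with WAZ correctly called weight-for-age. Section 7.3 defines WAZ as weight standardised for age and sex. The lead text of 9.4 reads "Secondary endpoint 4 & 5: To compare Δ WLZ and Δ MUAC in the 90 days following an episode", but 9.4.1, directly below it, defines ΔWLZ, ΔWAZ and ΔMUAC and makes all three model responses. Table 3 has ΔWAZ, ΔWLZ and ΔMUAC rows.

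**Version history (SAP section 1).** Version 00.5 records the addition of wasting outcomes, naming ΔWLZ and ΔMUAC only. Version 1.0 states that the SAP was aligned with the trial protocol. No entry mentions WAZ or the removal of weight.

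**The concern.** An endpoint that the protocol names and gives an analysis for has no analysis in the SAP, and an endpoint that the protocol never mentions stands in its place. A reader comparing the protocol with the trial report would find one secondary endpoint missing and one added, with nothing to say when or why. The statement of alignment in version 1.0 is not correct for this endpoint.

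The two measures are not interchangeable. The weight in kg that corresponds to one WAZ unit rises with age, so ΔWAZ is not a fixed multiple of Δweight across children aged 2 to 23 months. An effect that is constant in kg is uneven in z-units, and the reverse. The SAP's outlier rule (8.2) is also written in z-score bounds, with no rule for weight in kg. The two tests can therefore disagree; the question is how often.

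**Working it through.** **1. Tracing the endpoint**

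| Place | ΔWLZ | ΔMUAC | Δweight | ΔWAZ |
|---|---|---|---|---|
| Protocol 1.2, objective 1 | yes | yes | yes | no |
| Protocol 10.2, analysis | yes | yes | yes | no |
| SAP 3.2, items 4-6 | yes | yes | no | yes (misnamed) |
| SAP 5, hypotheses | yes | yes | no | yes |
| SAP 9.4, lead text | yes | yes | no | no |
| SAP 9.4.1, responses | yes | yes | no | yes |
| SAP Table 3 | yes | yes | no | yes |

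In the SAP tables, weight in kg appears only as a baseline characteristic. The gap is the Δweight column.

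**2. How often could the verdicts differ?** The documents give no SD, effect size or power for either measure, so there is no stated figure to reproduce.

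From the documents: 5,750 per arm less 10% loss, 5,750 × 0.9 = 5,175; alpha 0.05.

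Assumed:
- age *a* uniform over 2 to 24 months;
- kg per WAZ unit *s(a)* = 0.7 + 0.6(*a* − 2)/22, rising from 0.7 to 1.3;
- expected 90-day gain *g(a)* = 1.9 − 1.3(*a* − 2)/22 kg, falling from 1.9 to 0.6;
- SD of ΔWAZ 0.6;
- true effect δ constant in kg.

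Then Δweight = *g* + *sε* + δ·arm and ΔWAZ = *ε* + (δ/*s*)·arm, with *ε* ~ N(0, 0.6²).

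Moments: E[*s*] = 1.0; E[*s*²] = 1 + 0.6²/12 = 1.03; E[1/*s*] = ln(1.3/0.7)/0.6 = 1.032; Var(*g*) = 1.3²/12 = 0.141.

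Standard errors, √(2 × variance/5,175):
- ΔWAZ: variance 0.36, SE 0.0118.
- Δweight, unadjusted: 0.141 + 0.36 × 1.03 = 0.512, SE 0.0141 kg.
- Δweight, age-adjusted (removes *g*): 0.36 × 1.03 = 0.371, SE 0.0120 kg.

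Correlation of the test statistics:
- ΔWAZ with unadjusted Δweight: 0.36/(0.6 × √0.512) = 0.84.
- ΔWAZ with age-adjusted Δweight: 1/√1.03 = 0.985.

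Power at δ = 30 g, Φ(effect/SE − 1.96):
- ΔWAZ: 0.03 × 1.032/0.0118 = 2.62, power 75%.
- Unadjusted Δweight: 0.03/0.0141 = 2.13, power 57%.
- Age-adjusted Δweight: 0.03/0.0120 = 2.51, power 71%.

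Treating each pair of statistics as bivariate normal with these means and correlations, the share of trials in which exactly one test is significant at 0.05 is:

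| δ | unadjusted Δweight v ΔWAZ | age-adjusted Δweight v ΔWAZ |
|---|---|---|
| 20 g | 20% | 6% |
| 30 g | 22% | 6% |
| 40 g | 14% | 3% |

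Simulation under the same inputs gives about 15-23% unadjusted and 3-7% with age and age-squared as covariates (correlation 0.98; power at 30 g 76% for ΔWAZ and 72% for Δweight).

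**3. Sensitivity.** A separate unadjusted simulation set the effect on the z-scale (mean 0.03), for all ages or only for those under or over 12 months, with 0.7-1.2 or 0.8-1.3 kg per z-unit. Disagreement was about 16-31%, and about 6% with no effect. These runs also leave age in the error term of Δweight.

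**The case against.** **The names are only typos.** This stands. Item 5 of 3.2 carries the wrong name, but sections 5, 7.3, 9.4.1 and Table 3 all make WAZ weight-for-age. The lead text of 9.4 omits ΔWAZ, but its heading covers endpoints 4, 5 and 6, and 9.4.1 lists all three. A reader might infer that the SAP analyses weight-for-length twice, or leaves ΔWAZ unmodelled; the rest of the SAP rules this out.

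**The protocol's Δweight may have meant WAZ.** The protocol gives no unit. It does write z-score abbreviations (ΔLAZ, ΔWLZ) where it means z-scores, so plain weight is the natural reading. If WAZ was meant, the SAP still needs to say so.

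**ΔWAZ is a reasonable measure from the same weights.** This also stands. Standardising for age and sex suits a 2 to 23 month range and matches the approach to length. It justifies keeping ΔWAZ, but not the silent loss of the protocol endpoint.

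**The two analyses would nearly always agree.** This is largely true once Δweight is adjusted for age. The larger disagreement comes mainly from age-related growth left in the error term. The unadjusted comparison does follow protocol 10.2, which states no covariates. But SAP 4.3, 4.6 and 9.4.1 put country, baseline and clinic terms in the models for change outcomes.

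**A reader might infer a data-driven switch**, because SAP versions 00.6 to 1.0 follow the DSMB's June 2019 decision, which cited a difference in LAZ. The documents do not support that. The log does not show when WAZ entered, and SAP 6.2 keeps investigators blinded while the data for the main analyses are cleaned. A dated reason in the log would close the question.

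**Conclusion.** The point holds as one of fidelity to the protocol. Δweight is specified there and absent from every analytic part of the SAP; ΔWAZ replaces it, and the replacement is not logged.

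The effect on conclusions is small. For a true effect of 20 to 40 g, ΔWAZ and age-adjusted Δweight would give different significance verdicts in about 3-7% of trials, against about 15-23% if Δweight is unadjusted. Apart from the sample size, the 10% loss and alpha, these figures rest on assumptions: the kg-per-z curve, the growth curve, the SD of 0.6 and an effect constant in kg. They also omit the baseline, country and clinic terms. It would be wrong to infer that the weight conclusion is likely to change.

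Severity is minor. This is one of three components of one secondary objective; no primary endpoint or sample size depends on it, and ΔWLZ and ΔMUAC are retained.

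**What to change.** 1. Add Δweight (kg) to SAP 3.2, 5, 7 and 9.4 as the protocol-specified secondary endpoint, with a row in Table 3. Model it like the other change outcomes, with baseline weight and country, plus age. State that these covariates go beyond the protocol's plain regression.
2. State how implausible weights and children with bipedal oedema are handled for Δweight, since SAP 8.1 and 8.2 address only z-scores.
3. Keep ΔWAZ, labelled as introduced in the SAP, and record the change and its reason in the version history.
4. In passing, correct the name in 3.2 item 5 to weight-for-age and make the lead text of 9.4 list every endpoint analysed there.

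The cost is SAP wording, one extra model and one table row, on weights already collected.

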4.2 Per protocol (PP) analysis and definition of protocol deviation

The following participants will be excluded from the per protocol analysis:

- (i) participants with a primary outcome missing for each respective outcome
- (ii) Participants who have been non-adherent to treatment. Adherent participants are defined as those receiving all 3 doses of the study regimen in the first three days of trial participation. The exception to this is if a participant died during this 3-day period. Such participants will be included in the PP analysis.
- (iii) Participants whose follow-up visit for anthropometry was outside the window allowed by protocol will be excluded from per protocol analysis of Primary Outcome 2 (change in length-for-age z-score) and Secondary Outcome 1 (acute wasting), but will be included in Primary Outcome 1 (mortality).
- (iv) Participants who were ineligible or should not have otherwise been enrolled into the study

4.3 Accounting for stratified randomization by study site

The trial utilizes a stratified randomization scheme by country. As a result, all primary and secondary analyses will account for the randomization schema and adjust for country of enrolment by including unconditional fixed effects for country of enrolment in all analyses.

4.4 Sensitivity analyses examining potential baseline imbalances

We will report baseline characteristics of participants by trial allocation arm (Table 1), we will examine imbalance by trial arm, accepting that these arose by random chance, and will not conduct hypothesis tests for difference by allocation arm. However we will include any apparent imbalances in sensitivity analyses for all primary and secondary outcomes. In sensitivity analyses, we will include as model covariates characteristics which on univariable analysis are associated with the outcome of interest with a p-value <0.10 . If the point-estimates for the unadjusted and adjusted analyses of the primary outcomes differ by more than 10%, the adjusted analysis will be presented as primary.

